#### Serious adverse event

A serious adverse event (SAE) is defined as any AE that results in death, is immediately life-threatening, results in persistent or significant disability / incapacity, requires or prolongs

Proprietary confidential information.

© 2016 Boehringer Ingelheim International GmbH or one or more of its affiliated companies. All rights reserved.

This document may not - in full or in part - be passed on, reproduced, published or otherwise used without prior written permission.

patient hospitalisation, is a congenital anomaly / birth defect, or is to be deemed serious for any other reason if it is an important medical event when based upon appropriate medical judgement that may jeopardise the patient and may require medical or surgical intervention to prevent one of the other outcomes listed in the above definitions.

**Medical and scientific judgement should be exercised in deciding whether other situations should be considered serious reactions, such as important medical events that might not be immediately life threatening or result in death or hospitalization but might jeopardize the patient or might require intervention to prevent one of the other outcomes listed above. Examples of such events are intensive treatment in an emergency room or at home for allergic bronchospasm, blood dyscrasias or convulsions that do not result in hospitalization or development of dependency or abuse. Any suspected transmission via a medicinal product of an infectious agent is also considered a serious adverse reaction.**

*For Japan: An AE which possibly leads to disability will be reported as an SAE. Every new occurrence of cancer will be reported as a SAE regardless of the duration between discontinuation of the drug and the occurrence of the cancer.*

#### Intensity of adverse event

The intensity of the AE should be judged based on the following:

Mild:	Awareness of sign(s) or symptom(s) that is/are easily tolerated
Moderate:	Enough discomfort to cause interference with usual activity
Severe:	Incapacitating or causing inability to work or to perform usual activities

#### Causal relationship of adverse event

Medical judgment should be used to determine the relationship, considering all relevant factors, including pattern of reaction, temporal relationship, de-challenge or re-challenge, confounding factors such as concomitant medication, concomitant diseases and relevant history. Assessment of causal relationship should be recorded in the case report forms. *For Japan: The reason for the decision on causal relationship needs to be provided in the CRF.*

Yes: There is a reasonable causal relationship between the investigational product administered and the AE.

No: There is no reasonable causal relationship between the investigational product administered and the AE.

If an SAE is reported from a still blinded trial, the causal relationship must be provided by the investigator for all potential trial drugs, i.e. the BI trial drug and for all other trial drugs (i.e. any active comparator or placebo according to the trial design).

#### Worsening of underlying disease or other pre-existing conditions

Worsening of the underlying disease or of other pre-existing conditions will be recorded as an (S)AE in the (e)CRF.

#### Changes in vital signs, ECG, physical examination, and laboratory test results

Proprietary confidential information.

© 2016 Boehringer Ingelheim International GmbH or one or more of its affiliated companies. All rights reserved.

This document may not - in full or in part - be passed on, reproduced, published or otherwise used without prior written permission.

Changes in vital signs, ECG\*, physical examination and laboratory test results will be recorded as an (S)AE in the (e)CRF, if they are judged clinically relevant by the investigator.

\*Changes in the ECG indicating (silent) MI should be reported as a cardiovascular outcome event.

### Hypoglycaemic events

Hypoglycaemic events should be documented according to the following criteria:

- Asymptomatic hypoglycaemia: Event not accompanied by typical symptoms of hypoglycaemia but with a measured plasma glucose concentration  $\geq 54$  mg/dl and  $\leq 70$  mg/dl ( $\geq 3.0$  mmol/l and  $\leq 3.9$  mmol/l):
- Asymptomatic hypoglycaemia: Event not accompanied by typical symptoms of hypoglycaemia but with a measured plasma glucose concentration  $< 54$  mg/dl ( $< 3.0$  mmol/l)
- Documented symptomatic hypoglycaemia with glucose concentration  $\geq 54$  mg/dl and  $\leq 70$  mg/dl ( $\geq 3.0$  mmol/l and  $\leq 3.9$  mmol/l): Event accompanied by typical symptoms of hypoglycaemia
- Documented symptomatic hypoglycaemia with glucose concentration  $< 54$  mg/dl ( $< 3.0$  mmol/l): Event accompanied by typical symptoms of hypoglycaemia but no need for external assistance
- Severe hypoglycaemic episode: Event with any degree of documented hypoglycemia, requiring the assistance of another person to actively administer carbohydrate, glucagon or other resuscitative actions

All symptomatic hypoglycaemic events, all asymptomatic events with glucose levels less than 3.0 mmol/l and all asymptomatic hypoglycaemic events that are considered as adverse event by the investigator have to be recorded as an adverse event.

### Adverse Events of Special Interest

**The term AESI relates to any specific AE that has been identified at the project level as being of particular concern for prospective safety monitoring and safety assessment within this trial, e.g. the potential for AEs based on knowledge from other compounds in the same class. AESI's need to be reported to the sponsor's Pharmacovigilance Department within the same timeframe that applies to SAE.**

The following events are considered as adverse events of special interest (AESI):

- Hypersensitivity reactions such as angioedema, angioedema-like events, and anaphylaxis
- Skin lesions such as exfoliative rash, skin necrosis, or bullous dermatitis
- Hepatic events such as  $\geq 3$  fold ULN of AST and/or ALT in combination with an elevation of total bilirubin  $>2$  fold ULN measured in the same blood draw sample, hepatitis, hepatic injury, jaundice and potential Hy's Law cases.

**Proprietary confidential information.**

© 2016 Boehringer Ingelheim International GmbH or one or more of its affiliated companies. All rights reserved.

This document may not - in full or in part - be passed on, reproduced, published or otherwise used without prior written permission.

- Renal adverse events such as acute renal failure
- Pancreatitis (refer to the ISF)
- Thyroid neoplasm (benign)
- Thyroid cancer
- Pancreatic cancer

~~A list of terms that must be documented as AESI for each topic is provided in the ISF. The renal events and pancreatic events will be adjudicated by independent adjudication committees.~~

~~AESI's, even though they might be non-serious are to be documented in the eCRF within 24 hours of receipt and must be reported to the sponsor/CRO in an expedited manner similar to Serious Adverse Events. For details please see [Section 5.2.2.2](#).~~

**Protocol-specified AESIs (as identified by the investigator based on the above definitions for adverse events of special interest) can be classified as serious or non-serious but all these AESIs once identified by the investigator must be reported on an SAE form in an expedited manner similar to SAEs, even if they do not meet any of the SAE seriousness criteria.**

**Beyond of this, and for the purposes of ongoing pharmacovigilance activities by the sponsor, adverse events based on additional searches for coded preferred terms of adverse events captured in the trial database (such as Special MedDRA Queries (SMQs), and user defined searches (BicMQs)) will be queried to verify with the investigator if the adverse event reported represent a suspected or diagnosed protocol specified AESI. AESIs once identified by the investigator must be reported on an SAE form in an expedited manner similar to SAEs, even if they do not meet any of the SAE seriousness criteria.**

**These additional searches (summarized under the so called 'overview of protocol defined AESIs and safety topics of interest') may change according to active pharmacovigilance of linagliptin. The most up to date list of these searches will be included in the ISF and changes will be communicated to all investigators.**

#### *Hepatic events:*

Patients showing an elevation of AST and/or ALT  $\geq 3$  fold ULN combined with an elevation of total bilirubin  $\geq 2$  fold ULN measured in the same blood sample need to be followed up locally according to the "DILI checklist" provided in ISF.

#### *Renal events:*

~~Estimated creatinine clearance eGFR~~ will be calculated using the MDRD formula. This formula considers the race as an adjustment factor, therefore, the race must be known (and will be collected) for accurate estimation.

In case of an eGFR decrease of  $\geq 40\%$  since baseline (visit 2) and again in case of an eGFR decrease of  $\geq 50\%$  since baseline (visit 2) an additional visit 4-8 weeks after detection should

Proprietary confidential information.

© 2016 Boehringer Ingelheim International GmbH or one or more of its affiliated companies. All rights reserved.

This document may not - in full or in part - be passed on, reproduced, published or otherwise used without prior written permission.

be scheduled (unless detected at the EOT visit at study end) to collect a blood sample for repeat analysis of creatinine for calculation of the eGFR. An additional sample of creatinine should also be taken between the visits interval if a signal of increasing creatinine is reported to the study site by others (e.g., treating physicians from local labs).

*Skin lesions:*

If skin lesions occur (such as exfoliative rash, skin necrosis, or bullous dermatitis): further follow-up investigations should be done according to medical judgement depending on the clinical course until the patient is recovered and/or a diagnosis is made.

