C The study is event driven. The number of confirmed adjudicated primary endpoint events will be continuously monitored during the trial. Based on the available number of events the projected number of expected future events will be calculated. As soon as the projection reliably suggests that the total number of patients with a by adjudication confirmed primary endpoint event will reach 625 **611 within the next 24 weeks**, the trial team will perform respective actions to stop the trial. From this time point on, all patients are expected to perform their last visit (EOT visit) within the **regular proposed** time schedule, **which means within the next 24 weeks communicated via an investigator letter**. A follow-up visit will take place **one week 30 days** after the end of treatment (EOT visit).

Patients who discontinue study drug prematurely should continue study visits until study end. Study assessments may be omitted if a patient is willing to return to the pre-defined study visits, with exception **collection of adverse events, outcome events, concomitant therapy and laboratory testing of creatinine for the calculation of the eGFR**.

If a patient who prematurely discontinued study drug is not willing to return to the pre-defined study visits, at minimum a yearly telephone call (preferably every 6 months) and a telephone call at study end will be required, to document the occurrence of outcome events and vital status. If possible, other adverse events and concomitant therapy changes since last visit **might should** be recorded (refer to [section 3.3.4](#)).

D All patients will have a follow up visit **one week 30 days** following regular or premature completion of the treatment period. The follow-up visit may be performed as a phone visit for patients who did not prematurely discontinue study medication and who do not have abnormalities at the EOT visit (only adverse events/outcome events and changes in concomitant therapy to be obtained).

E Body Mass Index will be calculated automatically.

F A complete, head-to-toe physical examination (e.g. evaluation of the body and its functions using inspection, palpation, percussion, and auscultation) will be done.

G

H In addition to the visits indicated, electrocardiogram (ECG) should be recorded in case of respective cardiac symptoms (indicating rhythm disorders or cardiac ischemia).

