I For female patients (local urine pregnancy test in women of child bearing potential). More frequent testing can be done if required by local regulations/authorities.

J Distribution of glucometer and testing supplies with instructions at randomization (visit 2). During the treatment period, weekly finger stick glucose measurements are recommended (fasted). During the whole trial participation, additional measurements should be done if necessary and in case of hypo- or hyperglycaemia related symptoms. The patient should be instructed to bring their HBGM device and diary to the clinic for an additional measurement (fasted).

Proprietary confidential information.

© 2016 Boehringer Ingelheim International GmbH or one or more of its affiliated companies. All rights reserved.

This document may not - in full or in part - be passed on, reproduced, published or otherwise used without prior written permission.

K At visit 1 safety laboratory includes ALT, AST, alkaline phosphatase and creatinine to check for eligibility in addition to lipase, urine albumin, urine creatinine and HbA1c as specified in the [flow chart](#). At randomization (visit 2) baseline laboratory will be obtained. [See section 5.2.3](#) for to be obtained laboratory parameters. As of visit 6: yearly (every other visit) lipid profile (Total cholesterol, HDL cholesterol, LDL cholesterol and triglycerides), urine albumin and urine creatinine.

L Estimated ~~creatinine~~ **glomerular filtration rate (eGFR)** will be calculated using the MDRD formula. This formula considers the race as an adjustment factor, therefore, the race must be known (and will be collected) for accurate estimation. In case of an eGFR decrease of  $\geq 40\%$  since baseline (visit 2) and again in case of an eGFR decrease of  $\geq 50\%$  since baseline (visit 2) an additional visit 4-8 weeks after detection should be scheduled to collect a blood sample for repeat analysis of creatinine (eGFR). An additional sample of creatinine should also be taken between the visits if a signal of increasing creatinine is reported to the study site by others (e.g., GPs from local labs).

M In case of a stroke the reported value from the modified Rankin Scale will be collected approximately one week after stroke onset and 3 months after stroke onset. This might require an additional contact.

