
Proprietary confidential information.

© 2016 Boehringer Ingelheim International GmbH or one or more of its affiliated companies. All rights reserved.

This document may not - in full or in part - be passed on, reproduced, published or otherwise used without prior written permission.

if a patient is willing to return to the pre-defined study visits, with exception of collection of adverse events, outcome events, concomitant therapy and laboratory testing of creatinine for the calculation of the eGFR.

If a patient who prematurely discontinued study drug is not willing to return to the pre-defined study visits, at minimum a yearly telephone call (preferably every 6 months) and a telephone call at study end will be required, to document the occurrence of outcome events and vital status. If possible, other AE's and concomitant therapy changes since last visit might be recorded. Every attempt will be made by the investigator to ensure patients continue participating in the study during study drug interruptions and after discontinuation of study drug. The ITT analysis requires that all study patients be followed until study end even if the study drug was temporarily interrupted or discontinued.

Patients will have a follow up visit ~~one week~~ **30 days** following regular or premature completion of the treatment period. The follow-up visit may be performed as a phone visit for patients who did not prematurely discontinue study medication and who do not have abnormalities at the EOT visit (only AEs/outcome events and changes in concomitant therapy to be obtained).

In case early study termination is to be performed (e.g. based on recommendation by the Data Monitoring Committee [DMC]), a reasonable timeframe to stop the trial (perform last patient visits) will be defined and communicated to the investigators.

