#### *Visit 3 – EOT - FU*

- Clinical chemistry: creatinine and lipase
- Urine analysis: albumin and creatinine (visit 4, visit 6 and thereafter yearly).
- Clinical chemistry: cholesterol (total), HDL cholesterol, LDL cholesterol and triglycerides (visit 4, visit 6 and thereafter yearly)

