#### 5.2.3.1 Renal function

Renal function will be assessed by the central lab based on the plasma creatinine value measured according to the [Flow Chart](#). The eGFR will be calculated from serum creatinine using the following MDRD formula:

$$\text{eGFR} = 175 \times (\text{creatinine } (\mu\text{mol/L})/88.4)^{-1.154} \times \text{age}^{-0.203} \times (0.742 \text{ if female}) \times (1.212 \text{ if black})$$

Renal impairment will be classified in the following way:

No renal impairment: eGFR  $\geq$  90 mL/min/1.73m^2;

No renal impairment with evidence of kidney damage (**eGFR  $\geq$  90 mL/min/1.73m^2 and UACR  $\geq$  30mg/ g creatinine**);

Mild renal impairment: eGFR 60-89 mL/min/1.73m^2;

Moderate renal impairment: eGFR 30-59 mL/min/1.73m^2;

Severe renal impairment: eGFR 15-29 mL/min/1.73m^2;

ESRD: eGFR  $<$  15 mL/min/1.73m^2.

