## 6. INVESTIGATIONAL PLAN

### 6.1 VISIT SCHEDULE

All trial visits should take place preferably between 7:00 AM and 11:00 AM. If a patient mistakenly takes trial medication in the morning of a visit before attending the clinic or comes in non-fasted where a fasting condition is required (all visits except visit 1), the visit should be rescheduled for another day as soon as possible reminding the patient about the expected conditions. The rescheduled visit must take place in a short enough time-frame so that the patient has sufficient trial medication available.

All patients are to adhere to the visit schedule as specified in the [Flow Chart](#). Some flexibility is allowed in scheduling the visits according to visit time windows as specified in the [Flow Chart](#). If any visit has to be rescheduled, subsequent visits should follow the original visit date schedule (calculated from randomization visit 2).

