© 2016 Boehringer Ingelheim International GmbH or one or more of its affiliated companies. All rights reserved.

This document may not - in full or in part - be passed on, reproduced, published or otherwise used without prior written permission.

	
clinical trials in CKD and the current clinical landscape on decline in estimated glomerular filtration rate and subsequent risk of end stage renal disease and mortality.
 
Change 3: Overall MACE event rates are higher than initially expected and this allows reducing the sample size without major impact on study duration.
 
Change 4: Since the interim analysis for efficacy was deleted, the required number of patients with primary endpoint to achieve a power of 90% for non-inferiority is reduced from 625 to 611. The estimated trial duration increased slightly due to the change of the primary endpoint while ensuring a sufficiently long drug exposure for the last recruited patients.
 
Change 5: Since the primary endpoint was changed to 3-point MACE it is no longer listed as key secondary endpoint.
 
Change 8: For clarification
 
Change 9: For clarification

Section to be changed	Flow chart
Description of change	
Change 1: Change in follow-up period from 7 to 30 days
 
Change 2: Guidance revised on the timing of the EOT visit after study stop announcement after 611 endpoint events are reached
 
In addition
 

• ...changes since last visit might be recorded

 
Was changed into
 

• ...changes since last visit should be recorded

Proprietary confidential information.

© 2016 Boehringer Ingelheim International GmbH or one or more of its affiliated companies. All rights reserved.

This document may not - in full or in part - be passed on, reproduced, published or otherwise used without prior written permission.

	
Change 3: Footnote L: estimated creatinine clearance  Was changed into:  Estimated glomerular filtration rate

Rationale for change	
Change 1: To allow for outcome event data collection up to 30 days after EOT  Change 2: To clarify the respective actions to stop the trial when 611 endpoint events are reached  Change 3: For clarification

Section to be changed	Abbreviations

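### Does the differing wording on repeat creatinine after the study-end EOT visit leave late eGFR declines unconfirmed?

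*Protocol*

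**What the plan says.** Protocol 5.2.2.1 (Renal events) has two triggers for a repeat creatinine: an eGFR fall from visit 2 of at least 40%, and again one of at least 50%. The additional visit, 4-8 weeks after detection, should "be scheduled (unless detected at the EOT visit at study end) to collect a blood sample for repeat analysis of creatinine".

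Flow chart footnote L has the same two triggers and calls for "an additional visit 4-8 weeks after detection should be scheduled to collect a blood sample for repeat analysis of creatinine (eGFR"), with no exception for the study-end visit. Section 6.1 gives the flow chart force: "All patients are to adhere to the visit schedule as specified in the" flow chart.

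Three other provisions bear on the point:

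- **Follow-up visit.** The flow chart places it at EOT + 30 days (window +7) and marks eGFR and safety laboratory there. Section 5.2.3, under the heading covering visit 3 to follow-up, lists "Clinical chemistry: creatinine and lipase". Section 11 (amendment 2) gives the reason for the 30-day timing: "To allow for outcome event data collection up to 30 days after EOT".
- **Phone option.** Footnote D allows a "phone visit for patients who did not prematurely discontinue study medication and who do not have abnormalities at the EOT visit". Section 3.1 likewise limits it to patients "who do not have abnormalities at the EOT visit (only AEs/outcome events and changes in concomitant therapy to be obtained"), and 6.2.3 repeats the rule.
- **Endpoint.** SAP 5.2.1 requires a sustained decrease confirmed by adjudication. Protocol 10.2 and SAP section 5 leave event definitions to the CEC charter.

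**The concern.** Two current passages give sites different instructions for a drop first seen at the last on-treatment visit. A site working from 5.2.2.1 could conclude that no confirmation is wanted. A site working from footnote L would arrange a sample. Neither passage mentions the day-30 creatinine, the word abnormalities is not defined, and 5.2.3.1 says "Renal function will be assessed by the central lab based on the plasma creatinine value", so an EOT result could reach the site after the patient has left. If the follow-up were then done by phone, no second value would exist.

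The endpoint at stake matters. After non-inferiority is shown, the composite renal endpoint is tested for superiority at an initial one-sided level of 0.8 × 2.5% = 2.0%. A decline that adjudicators could not call sustained for want of a second value would be lost as an event, and the loss could depend on which text the site had read.

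**Working it through.** **1. What the exception removes.** The words in parentheses in 5.2.2.1 qualify the scheduling of an additional visit. They do not touch the follow-up creatinine in the flow chart and 5.2.3.

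**2. Timing.** The repeat window is 4-8 weeks, or 28-56 days. Follow-up is at day 30 to day 37 after EOT: 30/7 = 4.3 weeks and 37/7 = 5.3 weeks. The scheduled sample falls inside the window on every permitted day.

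**3. The two texts side by side, for a drop of at least 40% found at the study-end EOT visit.**

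| Follow-up done | Site follows 5.2.2.1 | Site follows footnote L |
|---|---|---|
| On site, day 30-37 | Creatinine drawn | Creatinine drawn, within the window |
| By phone | No second sample | Sample still due by day 56 |

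The instructions lead to different data only in the phone row. To reach it, the site must treat the patient as having no abnormality at EOT. A fall that the protocol itself names as a trigger under Renal events is hard to describe that way.

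**4. Late laboratory result.** No turnaround time is stated. The flow chart puts screening 14 days before randomization, and footnote A lets randomization proceed once the visit 1 laboratory results are known. The plan therefore appears to rely on central results within about two weeks, well before day 30. This is an inference.

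**5. Illustrative size.** First, the plan's own power (Protocol 7.6), from power = Φ(|ln HR|·√d/2 − z):

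- 432 events, HR 0.75, one-sided 2.5%: 0.2877 × 20.785/2 − 1.960 = 1.030, giving 84.8% (stated 85%).
- 210 events, HR 0.70, one-sided 2.5%: 0.3567 × 14.491/2 − 1.960 = 0.624, giving 73.4% (stated 73%).

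At the initial level of 2.0% (z = 2.054) these become 82.5% and 70.2%.

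Next, the share of events first seen at EOT. I simulated visits at day 84 and then every 168 days, follow-up uniform over 1.5-4.5 years (54 months' duration, 36 months' recruitment), and a renal rate of 2.5% a year × 0.875. Onset fell after the last scheduled visit before EOT in 7.4% of events; 7.5% is used.

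The remaining inputs are assumptions without support in the documents: 80% of patients on drug at study end, 80% of events eGFR-based, and 10-50% of those without a day-30 sample.

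- Events concerned: 0.075 × 0.8 × 0.8 = 4.8%, or 20.7 of 432 and 10.1 of 210.
- Without a second value: 4.8% × 0.1 = 0.48% (2.1 of 432; 1.0 of 210) to 4.8% × 0.5 = 2.4% (10.4 of 432; 5.0 of 210).

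| Events lost | Power, 432 events, HR 0.75 | Power, 210 events, HR 0.70 |
|---|---|---|
| none | 82.5% | 70.2% |
| 0.48% | 82.3% | 70.0% |
| 2.4% | 81.6% | 69.1% |
| 4.8% (none sampled at day 30) | 80.6% | 68.0% |

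**The case for a change.** The best case for changing the text is that the exception looks like a leftover. The amendment history shows follow-up moving from one week to 30 days after EOT and the renal threshold falling from 50% to 40%, while the parenthesis stayed. A charter can define how a decline is confirmed, but it cannot supply a sample that was never drawn. One linking sentence would remove the doubt without adding a visit or a sample.

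The share of events first seen at EOT is also uncertain. Dividing a 12-24 week gap by a mean follow-up of 2-3.5 years gives about 7% to 23%. If every one of 432 events were eGFR-based and none of that share were confirmed, 404 to 333 events would remain, and power at one-sided 2.5% would be about 82% to 75% instead of 84.8%.

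The textual part stands: the wordings differ and the link is unstated. The larger loss does not follow, because it requires the scheduled follow-up creatinine to yield nothing in any patient. Even the 50% missing share is hard to square with a phone rule that, read naturally, brings these patients to the site. The edit is also less cheap than one sentence suggests: it touches footnotes D and L, 3.1, 5.2.2.1 and 6.2.3, and under Protocol 8.1 amendments need ethics and authority approval, here for about 600 centres in up to 35 countries.

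**Conclusion.** No change to the plan follows. This is a wording mismatch, together with a gap that sites and adjudicators can fill sensibly from what is already scheduled. Followed as written, both texts lead to a creatinine at day 30-37. They part only where a follow-up is done by phone despite a large eGFR fall, which the phone rule on its natural reading does not allow.

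The effect cannot be determined from the documents. The illustration puts it at about one point of power or less, and about two points if no such patient had a day-30 sample, given a 7.5% share first seen at EOT. Follow-up rules are the same in both arms under blinding, so there is no evident route to bias.

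The conclusion rests on two readings: that a fall of at least 40% counts as an abnormality at EOT, and that EOT results reach sites before day 30. It also assumes that the CEC charter, which is not available here, lets adjudicators use the follow-up value. A charter that excluded that value would reopen the question.
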